This clinical investigation will gather trans-impedance and intra-cochlear voltage measurements intra- and post-operatively. These measurements can be used to characterise the electrical properties of the electrode array and the surrounding tissue in the cochlea after insertion. This data will be used to explore the specificity of the [name] candidate algorithm. Given the low incidence of anomalous electrode position cases in normal clinical practice (Dirr et al. 2013) and the inability to deliberately generate anomalous electrode positions in patients; this study is only focussed on exploring the specificity. (negative results divided by true negative cases) of the algorithm. An exploration of the sensitivity (positive results divided by true positive cases) of the candidate algorithm is out of scope for this study. A separate in vitro study where anomalous insertions can be purposely created will be conducted to explore the sensitivity.

 For statistical purposes, it is assumed that this study will show the algorithm able to achieve  $\geq 98\%$  specificity with a 90% confidence.

For the purpose of quantifying the accuracy of a diagnostic algorithm, the following terminology is used:

- Positive case – a case in which electrode insertion results in an anomalous position.
- Negative case – a case in which electrode insertion is successful and position is not anomalous.
- True positive response – The candidate algorithm correctly detects the presence of an anomalous electrode position.
- False positive response – The candidate algorithm incorrectly indicates an anomalous electrode position when none is present.
- True negative response – The candidate algorithm correctly indicates no anomalous electrode position when none is present.
- False negative response – The candidate algorithm fails to detect an anomalous electrode position even though one is present.
- Sensitivity - the number of true positive responses divided by the number of positive cases (anomalous positions).
- Specificity - the number of true negative responses divided by the number of negative (non-anomalous) cases.
- Positive predictive value – the probability that given a positive response the electrode position is anomalous
- Negative predictive value – the probability that given a negative response the electrode position is not anomalous

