The candidate algorithm is provided with the trans-impedance measurements and indicates whether a tip fold-over or array outside the cochlea have been detected. For the feedback from this algorithm to be clinically useful it must be shown that the specificity is sufficiently high to ensure that the surgeon is not unnecessarily prompted to take action (confirmation of electrode position by imaging) when not required. Current methods for detecting anomalous electrode position without relying on imaging either use manually-perceived force feedback from the electrode array (Dirr et al. 2013, Pile et al. 2013) or measurement of neural activity, (Grolman et al. 2008, Zuniga et al. 2016). Dirr et al. shows a positive predictive value of 29% using the sense of increased physical resistance during insertion whereas Grolman did not comment on the positive predictive value of the spread of excitation technique and Zuniga stated it was not clear. In the current study the aim is to show that using an algorithm based on the trans-impedance matrix a positive predictive value of twice that observed by Dirr et al. can be achieved, thus the aim is a positive predictive value of 60%.

Following the initial analysis as outlined in this investigation plan, future candidate algorithms developed for the purpose of detecting anomalous electrode position will be evaluated using the data as collected within the current investigation.

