The CT/DVT imaging before and after surgery and the CSEP measurements during and after surgery is part of the clinical routine in CI treatment and patients will be selected who follow this clinical routine.

In addition, the measurements, CT/DVT scans and classifications will be de-identified and stored in a database to support the further development and validation of algorithms. Those insertions showing the presence of anomalous properties will be excluded from the dataset that is presented to the candidate algorithm but will be included in this database. To allow for the exclusion of these insertions an additional 9 subjects are added to the study.

Depending on the recommended practice in the clinics the measures of surgeries performed by experienced and unexperienced surgeons will be collected. For retracement the name of the inserting surgeon is labelled on the surgical questionnaire.

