This entails that the false positive rate is no more than 2%, or that no more than 1 out of 50 insertions with normal position will be indicated as anomalous, and potentially receive medical imaging just to reveal that the insertion is normal. Assuming the incidence of tip fold-overs to be around 4% for pre-curved arrays, the 98% specificity will provide a positive predictive value of over 60% which meets the target positive predictive value from section 3.

In conclusion, 154 implantations are required.

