### 9.2 Candidate algorithm exploration

To explore the specificity of the candidate algorithm it will be provided with the trans-impedance data collected at surgery, first activation and 3 months post-operatively for insertions that has been determined not to contain any anomalous electrode array position based on the CT Scans.

In each instance the result of the algorithm will be analysed to determine the specificity based on the amount of positive and negative results returned by the algorithm.

---

 For the sample size calculation, it is assumed that the sensitivity (true positive) of the candidate algorithm is 90%.

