where n is the number of sufficient samples required to estimate specificity, N is the total sample size or number of patients required, i is the number of anomalies and p is the probability of an anomaly. We assume that the most prevalent anomaly condition will be a tip foldover. For p we use an estimate of 0.04139 or 4.14% which is based on the perimodiolar weighted average percentage between Grolman et al. (2009) and Zuniga et al. (2017). m is then approximately an upper bound on the number of expected tip fold-overs based on the 90th percentile of the cumulative binomial distribution. In other words, there is at least an approximate 90% chance that there will be m number of tip fold-overs or less.

Determining the sample size N is an iterative process. N is increased from 0 and for each value of N , n is calculated using Equations 3 and 4 which allows for P_{LB} to be calculated using Equation 1. Once P_{LB} is approximately 0.98 or 98%, the corresponding N is selected as the sample size.

Using the denoted method (see Appendix A) a sample size of $N = 154$ was selected which had a 89% chance of 9 or less tip fold-overs taking place, resulting in an $m = 9$ and $n = 145$. With a measured specificity (i.e. estimated specificity) of 100% and $n = 145$, the $P_{LB} = 0.9797$ which is approximately 98%.

With an algorithm target specificity of at least 98%, a target sensitivity of at least 90%, an estimated probability of a tip fold-over of 4.14%, the positive predictive value (PPV) is equal to 66.02%. This entails that after the algorithm has detected a tip fold-over, it is estimated that two thirds subset of patients will be confirmed by imaging to have a tip fold-over. The calculation of PPV is calculated by Equation 5:

$$PPV = \frac{(prevalence * sensitivity)}{(prevalence * sensitivity) + ((1 - prevalence) \times (1 - specificity))} \quad (5)$$

$$PPV = \frac{(0.0414 * 0.90)}{(0.0414 * 0.90) + ((1 - 0.0414) \times (1 - 0.98))} = 0.6602 \quad (6)$$

where in this application *prevalence* is the estimated rate of tip fold-overs.

3 Conduction of statistical analysis

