- A section storing intra-cochlear voltage measurements, the measurement parameters and the point in time the measurement was taken
- A section storing NRT measurements, the measurement parameters and the point in time the measurement was taken
- A section storing Cochlear Implant Fitting Software CDX files

An independent researcher (i.e. not the person who developed the database) will determine whether the information has been correctly uploaded to the database, the integrity of the data in the database and whether patient information has been sufficiently de-identified.

4 Quality control of statistical analysis

The statistical analysis plan will be undertaken primarily using the Python programming language with the Numpy and Scipy libraries. Other programming languages or software packages such as Matlab, SAS or Excel may also be used. The analysis plan will be:

1. Statistical analysis will take place once all of the data has been collected
2. Programmed to retrieve the objective outputs
3. The code and the outputs will be reviewed to determine whether or not what was stipulated in the objectives have been met and whether or not the outputs are in line with what domain experts' expectations

Code review and output review will be carried out by an independent person (i.e. not identical to the primary programmer).

If a patient has missing or spurious data, the data that is remaining of quality will be used in the clinical investigation. Patients that drop-out will cause only the data that has been collected to be analysed.

5 Derived data

All derived data as described in the conduction of the statistical analysis will be described in full detail with the steps taken to calculate or produce the derived data.

6 Analysis populations

All patients will be included in the analysis unless a patient has been confirmed to have an anomalous position.

7 Bibliography

Publication Of The American Otological Society, American Neurotology Society [And] European Academy Of Otology And Neurotology, vol. 38, no. 2, pp. 199-206.
Available from: 10.1097/MAO.0000000000001283. [15 March 2017]

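### Protocol section 3 sets a PPV aim that a specificity-only analysis cannot estimate, and SAP 3.1 leaves the order, masking and locking of the CT classification unsettled

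*Protocol*

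**What the plan says.** **On PPV**

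- Protocol section 3 sets the aim: "In the current study the aim is to show that using an algorithm based on the trans-impedance matrix a positive predictive value of twice" the 29% reported for an earlier method, which it takes as 60%.
- The same section says "this study is only focussed on exploring the specificity" and "An exploration of the sensitivity (positive results divided by true positive cases) of the candidate algorithm is out of scope for this study". Sensitivity is left to a separate in vitro study.
- Protocol 8.1: "Those insertions showing the presence of anomalous properties will be excluded from the dataset that is presented to the candidate algorithm". Protocol 9.2 and 9.3 repeat the restriction, and SAP section 6 states: "All patients will be included in the analysis unless a patient has been confirmed to have an anomalous position".
- Protocol 9.1: "Assuming the incidence of tip fold-overs to be around 4% for pre-curved arrays, the 98% specificity will provide a positive predictive value" above 60%, and it concludes that the section 3 target is met. Footnote 5 adds that "it is assumed that the sensitivity (true positive) of the candidate algorithm is 90" percent.
- SAP 2.2, with target specificity 98% and target sensitivity 90%: "an estimated probability of a tip fold-over of 4.14%, the positive predictive value (PPV) is equal to 66.02" percent.
- PPV is in no objective, endpoint, hypothesis or analysis step of either document.

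**On CT classification**

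- SAP 3.1 numbers its steps: run the algorithm (on patients with normal insertions), collect outputs, count the negatives, classify each insertion radiographically, then calculate the percentage and its lower bound.
- Protocol 8.1 and 9.2 put classification before the algorithm.
- Protocol section 5 gives the classification to an expert radiologist or ENT surgeon.
- Protocol 6.5 keeps algorithm outcomes from the investigators until official study closure. Protocol 6.2 has an independent party run the algorithm, and the analysis is done on de-identified data after closure.
- Protocol 9.3 excludes insertions with insertion-related events or poor medial-lateral position (the noun is missing in the text). It gives no cut-off for the second.

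**The concern.** PPV depends on specificity, sensitivity and prevalence, and this study measures only the first. A reader of Protocol section 3 or 9.1 could take a good specificity result as evidence that the PPV aim was reached, when the other two inputs are assumed or borrowed.

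The second part concerns the primary result itself. CT classification decides which insertions enter the specificity denominator. If a reader can see that the algorithm flagged an insertion, and one exclusion ground has no cut-off, a borderline scan may be called abnormal and leave the denominator. With a pass rule that tolerates no false positives, one such call changes the conclusion.

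**Working it through.** **1. The plan's own figures**

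Inputs from SAP 2.2 and Appendix A: 5 fold-overs in 0.48 × 303 = 145.44 arrays and 4 in 72; sensitivity 0.90; specificity 0.98.

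- Prevalence: 9 / 217.44 = 0.04139.
- PPV = prev × sens / [prev × sens + (1 − prev)(1 − spec)]. With 0.0414: 0.03726 / (0.03726 + 0.01917) = 0.6603. With the unrounded rate: 0.6602. The stated 66.02% is reproduced.
- Chance of 9 or fewer fold-overs in 154: 0.892 (stated 89%).
- Exact two-sided 90% lower bound for n of n correct: 0.05^(1/n). For 145 this is 0.97955; the Appendix A grid search gives 0.97975 (stated 0.9797).

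**2. What the study can contribute to PPV**

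The algorithm sees CT-normal insertions only. Every positive output there is a false positive, so the number of true positives is zero by design and PPV has no estimate. The projection moves with the two unmeasured inputs, specificity held at 98%:

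| Varied input | Value | Projected PPV |
|---|---|---|
| Prevalence (sensitivity 90%) | 2.2% | 50% |
| | 4.14% | 66% |
| | 7.1% | 78% |
| Sensitivity (prevalence 4.14%) | 50% | 52% |
| | 70% | 60% |
| | 90% | 66% |
| | 100% | 68% |

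The prevalence limits are the exact 90% interval for 9 of 217. Sensitivities other than 90% are assumptions. Reaching 60% at 4.14% prevalence needs sensitivity of at least 0.6 × 0.9586 × 0.02 / (0.4 × 0.0414) = 69.5%.

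**3. Order of steps**

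Step 1 of SAP 3.1 needs to know which insertions are normal; step 4 is where that is decided. The list is therefore inconsistent with itself, and step 4 also conflicts with Protocol 8.1 and 9.2.

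**4. How much one classification matters**

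Exact two-sided 90% lower bounds:

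| Correct / normal | Lower bound |
|---|---|
| 153/154 | 96.96% |
| 145/146 | 96.79% |
| 145/145 | 97.96% |

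Even with all 154 insertions normal, one false positive fails. With 146 normals and one flagged, calling that case abnormal gives 145 of 145. SAP 3.1 treats that as reaching 98%, though the exact bound is slightly below it. A literal 98% bound needs 149 of 149 (98.01%), and the same one-case dependence applies there.

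Illustration only: at a true specificity of 98% and 146 normals, P(no false positive) = 0.98^146 = 5.2% and P(exactly one) = 15.6%. If half of single flagged cases were relabelled, the chance of passing would be 5.2 + 0.5 × 15.6 = 13.0%; if all were, 20.8%. These proportions are assumed. The scenario needs at least 146 normals, which has a chance of 81% if fold-overs are the only exclusions.

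**The case against.** On PPV, the aim is one sentence of background. The same section limits the study to specificity, footnote 5 labels the 90% as assumed, and SAP 2.2 prints the formula and its inputs. No decision rests on PPV. All of that stands, and it limits this part to wording. A reader might infer that 66.02% is miscalculated; it is not. The fault is in claiming to show, and in Protocol 9.1 declaring met, something the data do not address.

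On classification, a reader might infer that the SAP intends scans to be read with outputs in hand, or that masking is absent. The documents do not support either. Step 1 and two Protocol sections imply classification first. Protocol 6.5 would cover a reader who is an investigator. Protocol 6.2 adds the independent party and de-identified data, and Protocol 9.3 extracts radiological parameters automatically. Step 4 requires a recorded reason for each abnormal reading, SAP section 4 has code and outputs independently reviewed, and Protocol 9.1 places final analysis after database closure. Because classifications are stored in the database, one can infer that they are fixed by then.

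What remains is that the lock is inferred and never stated. The CT reader is not named in the masking text. The blind ends at closure, which is when the steps of SAP 3.1 would be carried out.

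Protocol 6.2 also mentions runs at set intervals as well as analysis after closure. These could be two separate acts, so this is an ambiguity and not a proven contradiction.

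**Conclusion.** Both parts hold in limited form, and both should be corrected.

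1. The study cannot estimate PPV. Its 66.02% is a correct projection that ranges from 50% to 78% over the sampling uncertainty of the plan's own prevalence counts, and from about 52% to 68% for assumed sensitivities of 50% to 100%. The objectives and the primary test are unaffected.
2. SAP 3.1 contradicts itself and the Protocol on order, and no text expressly masks the CT reader or locks the classification before outputs exist. One relabelled case can move the lower bound from 96.8% to 97.96%, from fail to what the plan reads as pass.

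The 13.0% and 20.8% figures show leverage and are not error rates of this plan; nothing in the documents suggests that flagged scans would be re-read. Nor does it follow that the study should estimate sensitivity or PPV itself. The Protocol gives a reason for that exclusion, and with 154 × 0.04139 = 6.4 expected fold-overs the yield would be small: even 6 of 6 detected has an exact lower bound of 0.05^(1/6) = 60.7% for sensitivity.

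**What to change.** **Protocol sections 3 and 9.1.** Describe PPV as a projection conditional on the specificity found here, the sensitivity from the in vitro study and the prevalence. Show it over a range such as the one above, and remove the statement that the PPV target is met.

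**SAP 3.1.** Make radiographic classification the first step. State that the reader already planned is masked to algorithm output, that the classification is locked before the algorithm is run, and that one fixed algorithm version and threshold is then used. The last point matters because Protocol section 3 says the threshold still has to be explored.

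**Protocol 9.3.** Complete the wording of the medial-lateral exclusion and give its cut-off.

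**Protocol 6.2 and 8.1.** Say when the algorithm is run and when outputs are released. Align the 8.1 statement that all 154 insertions go to the algorithm with the later paragraph of 8.1 and with 9.2, which withhold anomalous ones.

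The cost is wording in both documents, and a masked read in a fixed order by the reader already planned. No extra patients, scans or analyses are needed, and specificity on CT-normal insertions stays primary.

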## 4 Identification and description of the devices

The following devices will be used in this investigation:

Implant	CI532, CI512	CE marked / TGA approved
Sound processor	CP900 series	CE marked / TGA approved
Software	CSEP 5	CE marked / TGA approved
Interface	Nucleus Programming Pod	CE marked / TGA approved

All hardware and software used in this clinical investigation has market approval in the European Union and in Australia. The use of all software and hardware in this clinical investigation is according to the current labelling and instructions for use.

The CSEP software, CP900 series sound processor and CI532 and CI512 implants are all used routinely by cochlear implant and hearing care professionals. The CP900 series sound processor is available at the clinic in case the recipient is aided with another sound processor. CSEP is incorporated in clinical routine to perform objective measurements which may help to create hearing profiles for cochlear implant recipients. All components will be available at the investigational sites as part of the clinical routine practice.

The Investigators will be trained on the trans-impedance and intra-cochlear voltage measurement that forms part of this study.

Please refer to the package insert and user guides of the devices for further information.

## 5 Justification for the design of the clinical investigation

Several researchers have demonstrated the utility of trans-impedance matrix and other voltage measurements (Hey et al. 2015, Vanpoucke et al. 2004, Vanpoucke et al. 2012) to identify the intra-cochlear electrode positioning. The current investigation is designed to both evaluate a candidate algorithm for detecting the occurrence of gross anomalies in position (e.g. tip fold-over or the electrode array not in the cochlea) and to provide a robust dataset in a clinically representative sample of cochlear implant recipients that can be used to test the specificity and sensitivity of future electrode position feedback algorithms. Such algorithms have potential clinical application in providing objective feedback to the surgeon at the time of electrode insertion to inform the surgeon on electrode placement without additional radiological imaging, and may in future lead to improved clinical outcomes for cochlear implant recipients.

No large database of combined high quality imaging of the intra-cochlear electrode position and reliable trans-impedance measurements exist. It is only relatively recently that it has become possible to determine accurate intra-cochlear electrode position, as a result of advances in scanner technology. Also, the trans-impedance measurements (contained in Custom Sound™ Electro Physiology) that will be used in the study only recently became available. Earlier versions of this tool did not provide sufficient resolution to accurately measure the electrical spread curves.

To explore the decision algorithm, a large dataset is needed. This study will systematically collect a large pool of trans-impedance measurements of CI recipients combined with state of the art imaging of the implanted electrode as part of the clinical routine. Image analysis will allow an expert radiologist/ENT surgeon to determine for each implantation whether it is a normal case or not. The trans-impedance measurements will be analysed by the decision algorithm, and the agreement with the human experts will be established. This exploration of the specificity of the candidate algorithm is the main target of this study, thus being evaluated on the bench without patient involvement.

At this point in time, little is known about the stability of the trans-impedance measurements over time. In the first months after implantation, the electrode will be encapsulated in a tissue sheath. Our assumption is that this may influence the electrical spread curves and therefore the performance of the classification algorithm. The study design therefore includes two post-operative measurements. During these sessions, the response of the auditory nerve to electrical stimulation will be monitored as well with a technique known as neural response

---

 Where the electrode array tip turns back on itself during insertion into the cochlea.

telemetry (NRT). The study visits that are performed are in line with routine clinical practice, to minimise the additional commitment required by subjects and clinicians in participating in the required test sessions.

The study participants will be recruited from adults CI candidates in the participating study centres. Since the cochlear anatomy in children is identical to adults and the same electrode types are used, there is no need to include children in the study.

